9.1.3 Tertiary endpoint(s)

Tertiary endpoints, related to patient treatment history, will be evaluated. The tertiary endpoints for patients who received sorafenib prior to regorafenib are:

- Duration of sorafenib treatment, defined by the time interval from the start of sorafenib treatment to the day of permanent discontinuation of sorafenib
 - Reasons for sorafenib discontinuation will be recorded, as will doses of sorafenib given and time from sorafenib initiation to death, including time on regorafenib
- Response to sorafenib treatment, as assessed using mRECIST
- Overall survival, defined as the time interval from the start of sorafenib treatment to death due to any cause
- Frequency of adverse reactions experienced during treatment with sorafenib
- Time from discontinuation of sorafenib to start of regorafenib

Tertiary endpoints for prior treatments other than sorafenib are defined analogously.

9.1.4 Strengths of study design

The international, observational study design enables data to be collected from patients treated under local standard-of-care clinical practice; all decisions in terms of diagnostic procedures, treatments, management of the disease, and resource utilization are fully dependent on mutual agreement between the patient and the attending physician, without interference by the study protocol. This will enable assessment of treatment and subsequent outcomes based on local standards, and is likely to encompass a wider range of therapeutic decisions compared with the stricter, defined limits on therapy required by investigational study protocols. Decisions and outcomes made in real-world conditions are likely to be more applicable to wider clinical practice than those from interventional studies.

This study population is larger and likely to be more diverse than that observed in prior interventional trials, with a broader range of disease severity, prior treatments, comorbidities and concomitant medications. The sample size will enable comprehensive characterization of the regorafenib safety profile of all treated patients, as well as analysis of safety and effectiveness among different patient subsets (for example, by Child–Pugh status, prior treatment history).

9.2 Setting

9.2.1 Eligibility

Patients with uHCC and for whom a decision to treat with regorafenib has been made (by the treating physician) will be eligible for enrollment into the study. Patients considered for study enrollment and treatment with regorafenib should meet the criteria for regorafenib use according to the local health authority-approved product information, including indications and contraindications with respect to the local market authorization / summary of product characteristics (SmPC).

9.2.2 Inclusion criteria

- Patients with confirmed diagnosis of unresectable HCC
- Physician-initiated decision to treat with regorafenib (prior to study enrollment)
- Signed informed consent form

9.2.3 Exclusion criteria

- Participation in an investigational program with interventions outside of routine clinical practice
- Past treatment with regorafenib

9.2.4 Withdrawal

In this observational study, withdrawal from the study is independent of the underlying therapy and will not affect the patient's medical care. Each patient can refuse to further participate or may withdraw from the study at any time and without giving a reason. If a patient wants to terminate the study participation, no further data will be collected. However, the patient will be asked whether he/she agrees that the data collected so far can be used. In case the patient does not agree, these data will not be used for any patient level analysis of study data. This includes safety data, with the exception that data already captured in the company's safety database, which will be kept. However, data that are relevant for primary outcomes might be displayed on an aggregated level to assess a potential bias. In case a patient would like to withdraw the consent given earlier, he/she should inform his/her doctor and the site should document the withdrawal in the CRF as well as in the patient's medical records.

9.2.5 Replacement

Patients will not be replaced.

9.2.6 Representativeness

The patients documented in the study should be selected based only on eligibility according to inclusion and exclusion criteria (sections 9.2.1 - 9.2.3). No further selection should be applied. Physicians will be asked to sample consecutive patients whenever possible to avoid selection bias and thus increase the likelihood of representativeness. At each site, all screened patients will be documented consecutively in an anonymous screening log with reasons for non-participation (without recording patient-specific data).

9.2.7 Visits

The start of the study is the date from which information on the first patient can be first recorded in the study dataset (i.e. first informed consent obtained). The end of the study is the date after which the final patient remaining in the study has been in the study for 24 months, or is no longer under observation owing to being lost to follow-up, withdrawal, or death.

A visit is defined as any status assessment or new treatment decision the treating physician takes in the presence of the patient. The time interval between two documented status assessments is assumed to be 6–12 weeks, although this will be at the discretion of the treating physician.

The investigator will document the baseline / initial visit, follow-up visits and the end of observation / final visit for each patient in the CRF. Follow-up visits occur during routine practice; the study protocol does not define exact referral dates for those visits. The end of observation / final visit is to be documented after a patient has been on study for at least 24 months, is lost to follow-up, has withdrawn consent or has died, whichever comes first. If the documentation is stopped prematurely, the reasons for the end of observation must be given. If a patient joins an interventional clinical study during the course of observation, information on survival should be collected up to the end of this study. If a patient remains alive at time of study closure, this will be documented in the final visit.

Table 3: Tabulated overview on variables collected during the study

Variables	Baseline / Initial visit*	Follow-up visit(s)	End of observation / final visit
Visit date	X	X	X
Eligibility assessment	X		
Patient information and consent	X		
Demography	X		
Co-morbidities (medical history, concomitant diseases)	X		
HCC classification	X		
Prior systemic anti-cancer therapy (including sorafenib) (see 9.3.3.6)	X		
Tolerability of prior systemic anti-cancer therapy (including sorafenib) (see 9.3.3.6)	X		
Prior local anti-cancer therapy	X		
Prior medication	X		
Lifestyle records (smoking & alcohol use)	X		
Vital signs	X		
BCLC Staging	X		
Tumor status and metastases (see 9.3.3.9)	X	X	X
Child-Pugh classification	X	X	X

ECOG performance status	X	X	X
Laboratory parameters (see 9.3.3.7)	X	X	X
Concomitant medication	X	X	X
Exposure/treatment with regorafenib (see 9.3.3.8)	X	X	X
Adverse events on regorafenib (see 9.3.3.11)	X	X	X**
Reason for end of observation			X
Death and reason for death			X
Survival assessment			X

^{*}Initial visit is the visit when treatment with regorafenib is started. Baseline and Initial visit can be at the same day

9.3 Variables

The investigator collects historic data (demographic and clinical characteristics) from medical records if available, or else by interviewing the patient. Likewise, the investigator collects treatment related data during initial visit and follow-up visits. The investigator documents the study-relevant data for each patient in the CRF. The CRF is available upon request (see Table 4, Annex 1).

Information will be collected from laboratory tests performed according to the local standard of care. For potential TEAE reporting of any laboratory abnormalities please refer to section 11.

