	To evaluate the safety of regorafenib in patients with uHCC, including incidences of all treatment-emergent adverse events (TEAEs) and dose modifications due to TEAEs under real-world practice conditions.			
	Secondary objectives are:			
	• To describe the effectiveness of regorafenib, including overall survival (OS), progression-free survival (PFS), time to progression (TTP), and overall tumor response (ORR)			
	• To describe the patterns of regorafenib treatment, including actual doses, duration of treatment (DOT), and other dosing parameters			
	To describe patient characteristics, comorbidities, and their influence on treatment and outcomes under real- life conditions			
	To describe physicians' practice patterns, including regional difference in the management and treatment of uHCC under real-world conditions			
	Tertiary objectives are:			
	To describe sorafenib treatment prior to regorafenib treatment, including doses, duration of treatment, best response, and reasons for discontinuation			
	 To describe other therapies for HCC prior to regorafenib, including doses, duration of treatment, best response, and reasons for discontinuation (in relevant patients) 			
Study design	International, prospective, open-label, multicenter, observational study.			
Population	Female and male patients with a diagnosis of uHCC in whom a decision to treat with regorafenib has been made by the treating physician at the time of study enrollment.			
Variables	Variables for the primary objective are adverse events (AEs). Variables for secondary and tertiary objectives are demography, HCC classification, medical history/comorbidities, prior systemic anti-cancer therapy and tolerability (including sorafenib), prior local anti-cancer therapy, prior medication, lifestyle records, vital signs, tumor status and metastases, Child–Pugh classification, BCLC staging, ECOG performance status, laboratory parameters,			

	treatment with regorafenib (including AEs), and reason for ending the treatment and/or observation (including death). Other variables include eligibility for the study, informed consent and visit dates.	
Data sources	Treatment-related data are documented during visits that take place in routine practice. Historic data are based on medical records or on interviewing the patient.	

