9.3.3.6 Prior and concomitant medication

All medication taken before study start (initiated and stopped before study start) is termed prior medication. Prior medication meeting the criteria listed below are considered to be relevant to the study indication must be documented:

- Treatment for HCC
 - o Previous treatment with systemic therapy (including sorafenib)
 - Drug name
 - Start and stop date
 - Dose(s), including maximum tolerated dose
 - Therapy type and intent of treatment
 - Best response to treatment
 - Date of radiological progression, including type of progression (new lesion, new vascular invasion, progression of target lesion and quantification)
 - Tolerability of systemic treatment, including dose modifications relating to side effects

- Reason for discontinuation
- Previous local therapy
 - Procedure, drug name, dose, embolization agent, and intent
 - Administration date
 - Anatomic location
 - Best response to treatment
- Treatments for indications other than HCC

All medication taken in addition to regorafenib for any indication (either initiated before study start or during the study) is termed concomitant medication and has to be documented.

Information to be collected for medication includes:

- Trade name or INN
- Start date, stop date/ongoing
- Dose
- Unit
- Indication

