9.4 Data sources

The investigator collects historic data (demographic and clinical characteristics) from medical records if available. Likewise, the investigator collects treatment-related data during visits that take place in routine practice. Each patient is identified by a unique central patient identification code, which is only used for study purposes. For the duration of the study and afterwards, only the patient's treating physician or authorized site personnel are able to identify the patient based on the patient identification code.

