9.9 Limitations of the research methods

Because of the non-interventional study design and limitations inherent to observational studies, findings generated from this study are subject to biases, such as selection bias, limitations to availability of historical medical data, and differences in treatment or reporting owing to local guidelines.

Results for secondary effectiveness variables PFS or TTP must be interpreted carefully because of the uncontrolled setting: time periods between follow-up visits are more variable than in controlled

clinical studies, in which a fixed visit schedule is maintained. The quality of the tumor status evaluation will differ from that in controlled clinical studies.

Comparison of outcomes after treatment with regorafenib versus treatment with a comparator cannot be performed in this single-arm study. Comparisons can only be performed with historical data from clinical or observational studies, which is prone to bias and confounding. Historical patient data collected with respect to prior sorafenib or other treatments may be incomplete and/or differ relating to sorafenib use and standard of care in local practice. Historical data provided by patient interview is prone to errant recall.

Although the study aims to include participants from a variety of geographic regions, there may be local limitations that reduce the representativeness of patients recruited, such as patient access to recruiting physicians (including differences in patient profile in specialized, recruiting sites vs local general practice), regorafenib availability and reimbursement, and decisions relating to local standard of care. In addition, the planned patient sample size to be recruited from Japan (150 patients) may result in comparative over-representation from this country with respect to other individual nations.

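### Response to prior sorafenib is labelled mRECIST-assessed, but the permitted sources include patient interview and no response criterion is listed for collection

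*Protocol*

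**What the plan says.** **Endpoint.** Protocol section 9.1.3 lists, for patients who received sorafenib before regorafenib, "Response to sorafenib treatment, as assessed using mRECIST". It adds: "Tertiary endpoints for prior treatments other than sorafenib are defined analogously".

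**Source.** Section 9.3 says historic data come "from medical records if available, or else by interviewing the patient". The data-sources row of the abstract (section 4) puts it as "Historic data are based on medical records or on interviewing the patient". Section 9.4 says "The investigator collects historic data (demographic and clinical characteristics) from medical records if available" and does not mention interview.

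**Items collected.** For previous systemic therapy, section 9.3.3.6 lists a best-response entry and "Date of radiological progression, including type of progression", the type covering new lesions, new vascular invasion and quantified target-lesion progression. Neither a response criterion nor the source of the value is listed. Section 9.3.3.4 requires TNM, BCLC and Child–Pugh status at the start of sorafenib, where applicable.

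**Analysis and limitations.** Section 9.7.5 summarizes sorafenib response descriptively from retrospective data. Section 9.9 warns that prior-treatment data may be incomplete and that "Historical data provided by patient interview is prone to errant recall".

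**The concern.** mRECIST is an imaging criterion, so a patient interview cannot yield an mRECIST category. Nor can it reliably supply the date and type of a radiological progression, or a stage or Child–Pugh class at an earlier time point. The general source rule nevertheless covers these items by default, because nothing takes them out of it. Sections 9.3.3.4 and 9.3.3.6 require such history to be documented, and the protocol gives sites no instruction to enter not available when the record is missing.

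The label is also insecure where a record does exist. A best response recorded in routine care may have been assessed by another criterion or by clinical judgment, and the listed variables do not show which.

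What is at stake is the meaning of a reported result. A table headed as mRECIST response to sorafenib could mix mRECIST readings, readings by other criteria and recollection. A reader of the study report would take all of it as mRECIST. The same applies to other prior therapies, through the extension by analogy.

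**Working it through.** This is mainly a comparison of sections.

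1. **Label against source.** Section 9.1.3 applies the mRECIST label to prior response without qualification. Section 9.3 and the abstract allow interview as the fallback. Neither excludes tumor response or progression. A recalled response therefore satisfies the source rule while failing the endpoint definition.

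2. **Label against variable.** Section 9.3.3.6 collects best response with no criterion, and section 9.3.2 likewise names only best tumor response to sorafenib. From the listed items alone, one cannot tell which responses meet the definition in 9.1.3.

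3. **Prior against on-study response.** For regorafenib, section 9.3.3.9 accepts whatever criteria local guidance uses, and section 9.7.4 makes mRECIST a preference subject to local standard. The retrospective assessment, where the study has least control, thus carries the firmer label.

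4. **Progression.** Sections 9.3.2 and 9.3.3.6 call prior progression radiological, not mRECIST. A recalled date would be wrongly presented as radiological, and no more than that.

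5. **9.3 against 9.4.** The two sentences agree on records. Section 9.4 is silent on the fallback. This is an omission, not a conflict.

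6. **Size.** Let p be the response rate that records would give, q the apparent rate among interview-sourced patients and s the share sourced by interview. The pooled rate is (1 − s)p + sq, so the shift is s(q − p). The protocol gives none of the three.

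   For illustration only, assume p = 10%, and that recall has sensitivity 80% and specificity 85%:
   - q = 0.10 × 0.80 + 0.90 × 0.15 = 0.215
   - s = 10%: 0.90 × 0.10 + 0.10 × 0.215 = 0.1115, a shift of 1.15 points
   - s = 20%: 0.80 × 0.10 + 0.20 × 0.215 = 0.1230, a shift of 2.30 points
   - s = 30%: 0.70 × 0.10 + 0.30 × 0.215 = 0.1345, a shift of 3.45 points

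   Even the direction depends on the assumptions. With p = 10% and sensitivity 80%, q equals p when the false-positive rate is (0.10 − 0.08)/0.90 = 0.022, that is, at specificity of about 97.8%. Above that, recall would lower the pooled rate.

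7. **Sample size.** The only quantitative planning figures, in section 9.5, concern adverse events. They reproduce: for a true incidence of 0.2%, 1 − 0.998^1000 = 0.8649, as tabulated. They do not depend on this point and would not change with its correction.

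**The case against.** The strongest reply has four parts.

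- **The source sentence is general.** It describes historic data as demographic and clinical characteristics and puts records first. No section tells an investigator to ask a patient for a tumor response. That is right: interview is permitted for these items by default and is not prescribed. But section 9.9 places its recall warning directly after its remarks on prior-treatment data, so interview-sourced history is expected.

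- **The limitation is disclosed.** It is. Disclosing recall error does not make a recalled value an mRECIST assessment, and section 9.9 gives no handling rule.

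- **Other documents may deal with it.** The CRF was a separate draft (v.06, Annex 1) and is not shown; it may hold fields for source or criterion. Handling of missing data is left to the data management plan and SAP. Section 9.8.2 plans verification against source for at least 125 patients, 12.5% of 1000, which could expose unsupported values in that sample only. So one cannot say that recalled values will be inseparable from recorded ones. The endpoint wording and the source rule, however, are fixed in the protocol.

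- **Records-only collection trades recall error for missingness**, which may also vary by site. This stands as a real cost.

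A reader might also infer that interview use will cluster in certain regions and create false regional differences, or distort regorafenib results stratified by sorafenib response. The protocol supports neither inference. It says nothing about where records will be lacking. Its specific sorafenib-based analyses use prior dose or dosing pattern and adverse reactions (sections 9.7.4 and 9.7.5), and stratification by prior treatment appears only in general terms (section 9.7.1).

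**Conclusion.** The point holds. The protocol attaches an mRECIST label to prior response that neither its permitted sources nor its listed variables can guarantee. Followed as written, it can report recalled or non-mRECIST responses as mRECIST, and recalled progression dates as radiological.

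The consequence is limited. The outcomes are tertiary and descriptive, no hypothesis is tested, and the primary safety endpoint is untouched. The size is unknown, since the shifts of 1.15 to 3.45 points shown above rest wholly on assumed inputs. The conclusion itself rests on the text alone and needs none of those figures. A source or criterion field in the CRF would ease the practical problem, but the wording of 9.1.3 would still need correction.

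**What to change.** - **Sections 9.3 and 9.4, in matching terms:** take best response and the date and type of radiological progression on prior systemic therapy from medical records only, together with Child–Pugh, BCLC and TNM at sorafenib start. Where no record exists, enter not available. Interview can remain the fallback for other history, such as lifestyle.
- **Section 9.1.3:** restate the endpoint as best response to sorafenib as documented in the medical record, described as mRECIST only where the record says so. The same wording then carries over to other prior therapies.
- **CRF:** record the response criterion and the source of the value, if it does not already do so.
- **Reporting:** give the number of not-available entries beside the response table.

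The cost is a wording amendment, at most two CRF fields, and fewer patients with a prior-response value. That loss may differ between sites, which is why the count should be shown.

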9.3.1 Variables to determine the primary endpoint(s)

The variables for the primary objective are:

- AEs and SAEs
- TEAEs leading to dose modifications (including reductions, interruptions and permanent discontinuation)

9.3.2 Variables to determine the secondary and tertiary endpoint(s)

The outcome variables for secondary objectives are:

- Demographic data and disease history
- Regorafenib use (including start/stop dates and dosage)
 - o Initiation and termination dates
 - Dosage and dose modification
- Tumor assessment after initiation of regorafenib
- Date of radiological or clinical progression on regorafenib
- Child–Pugh score
- ECOG performance status
- Laboratory examination data
- Date of death

^{**}Adverse events (up to 30 days after the final treatment with regorafenib/ last treatment within the observation period)

Outcome variables for tertiary endpoints include:

- Sorafenib treatment history (prior to study entry)
 - o Initiation and termination dates
 - o Tolerability of sorafenib treatment
 - Radiological progression on sorafenib
 - o Best tumor response to sorafenib
- Previous systemic therapy other than sorafenib
 - o Initiation and termination dates
 - Tolerability of systemic therapy
 - Radiological progression on therapy
 - Best tumor response to therapy

